11.3 Electrocardiogram

A central vendor with readers blinded to treatment assignment will perform the reading of the ECGs. The central ECG results will be used for the statistical analyses.

Descriptive statistics for ECG parameters (heart rate, RR interval, PR interval, QRS interval, QT interval, and QTc interval) at baseline, 30 to 90 minutes after the start of the first infusion of the first and third doses of test article, Day 7 (+1 day), and at the EOT Visit, and the change from baseline will be presented by treatment group. The QTc interval will be presented by both the Bazett ($QTcB = QT/(RR)^{1/2}$) and the Fridericia ($QTcF = QT/(RR)^{1/3}$) corrections. The change from baseline to the minimum and maximum post-baseline values will also be summarized by treatment group. Baseline is defined as the value closest to but prior to the initiation of test article administration. If no value is available prior to the initiation of test article administration, a value within 2 hours after initiation of test article administration.

The number and percentage of subjects with any post-baseline increase in QTcF and any post-baseline increase of > 30 msec or > 60 msec in QTcF will be summarized by treatment group. The number and percentage of subjects with a baseline QTcF ≤ 450 msec and with a post-baseline QTcF of > 450 msec and with a baseline QTcF ≤ 500 and with a post-baseline QTcF of > 500 msec will also be summarized by treatment group. The number and percentage of subjects with a post-baseline increase in QTcF of > 30 msec resulting in a post-baseline QTcF of > 450 msec or > 500 msec will also be summarized by treatment group. A listing will also be provided of subjects with a QTcF that meets one of the criteria listed above and will list all QTcF values for the subject.

The distribution of QTcF values (≤ 450 msec, $> 450 - \leq 480$ msec, $> 480 - \leq 500$ msec, and > 500 msec) at each time point and the distribution of change from baseline in QTcF values at each time point (0 or less [no increase], 1-29 msec, 30-60 msec, and > 60 msec) will be summarized by treatment group.

11.4 Laboratory Values

Summaries of laboratory data will include hematology, chemistry, and coagulation (INR only) parameters. Laboratory parameters will be presented in alphabetic order with the following exceptions: differentials of white blood cell (WBC) counts will be presented following the WBC results, and chemistry parameters will first be grouped by organ class (renal, liver, electrolytes, and other) and presented alphabetically within each of these classes, as shown below.

Table 9. Laboratory Parameters and Organ Class

Organ Class	Laboratory Parameter
Renal	Creatinine
Renal	Urea
Liver	Alkaline phosphatase (ALP)
Liver	ALT
Liver	AST
Liver	Total Bilirubin
Liver	GGT
Electrolytes	Bicarbonate
Electrolytes	Calcium
Electrolytes	Chloride
Electrolytes	Magnesium
Electrolytes	Potassium
Electrolytes	Sodium
Other	Albumin
Other	Amylase
Other	Blood glucose
Other	Cholesterol
Other	CK
Other	LDH
Other	Lipase
Other	Phosphate
Other	Total protein
Other	Uric acid

Baseline is defined as the central lab value closest to and prior to the first dose of study drug. If no central lab value is available prior to the first dose of study drug, the local lab value that is closest to and prior to the first dose of study drug will be used as baseline. For by visit analyses, central lab values will be used unless no central lab value was obtained in the visit window. In this case, local lab values will be used for the by visit analyses. All lab values (central and local) are used for determination of the overall worst post-baseline value.

Several analyses of the laboratory data will be presented. Descriptive statistics (based on International System [SI] units) for chemistry, hematology and coagulation values, and the change from baseline will be summarized by treatment group at each time point (Day 4 [+1 day], Day 7 [+1 day], Day 10, EOT Visit and PTE Visit), and for the overall worst value

post-baseline (which includes unscheduled visits). [Appendix 4](#) provides the directionality of the worst values for each laboratory parameter.

Clinically notable laboratory values will be determined based on the modified Division of Microbiology and Infectious Diseases (DMID) criteria in [Appendix 5](#). Shift tables will be presented to show the number of subjects with a laboratory value with a grade of 0, 1, 2, 3 or 4 at baseline versus the value at each visit and the worst post-baseline value. Number and percentage of subjects with at least a 2-grade increase from baseline (based on DMID criteria) will be summarized by treatment arm. Percentages for each laboratory test will be based on the number of subjects with a baseline and post-baseline evaluation of the specific laboratory test. A listing will be provided which gives all laboratory results for a given laboratory test for subjects who have at least one 2-grade increase from baseline.

The number and percentage (based on the number of subjects with a normal level at baseline) of subjects in each treatment group with an elevated transaminase level ($> 3 \times$ upper limit of normal [ULN], $> 5 \times$ ULN, and $> 10 \times$ ULN), an elevated bilirubin level ($> 1.5 \times$ ULN and $> 2 \times$ ULN) will be presented by study visit. A listing of subjects who meet the laboratory criteria for Hy's law at the same visit will also be provided. The laboratory criteria for Hy's law is defined as 1) ALT or AST $> 3 \times$ ULN, ALP $\leq 2.0 \times$ ULN, and total bilirubin > 1.5 ULN and 2) ALT or AST $> 3 \times$ ULN, ALP $\leq 2.0 \times$ ULN, and total bilirubin $> 2 \times$ ULN.

Detailed subject listings of all laboratory data collected during the study (local and central laboratory data) will be provided, including calculated creatinine clearance (using the Cockcroft-Gault equation). Laboratory values outside normal limits will be identified in the subject data listings with flags for low (L) and high (H) as will laboratory values that meet the clinically notable thresholds (CN).

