An increase in mean heart rate was observed, but to a much lesser extent than what was observed in Phase 1 studies. During the first 4 hours following the start of the first infusion of omadacycline there was a mean increase in heart rate from Baseline of 2.5 bpm for omadacycline (range from -20 to 40 bpm), peaking at 4 hours, as compared to a slight decrease of -0.1 bpm effect on heart rate for the linezolid treatment arm (range from -21 to 22 bpm), $p = 0.005$. This effect was transient and no QT prolongation was observed, consistent with the omadacycline thorough corrected QT interval (QTc) and human Ether-à-go-go-Related Gene (hERG) studies. Three subjects treated with omadacycline had AEs of tachycardia; 1 other subject reported palpitations. All 4 of these AEs were mild in intensity, all were assessed as either unrelated or unlikely related to test article, and none resulted in discontinuation of study treatment. Three of these AEs occurred during the first week of treatment; 1 AE occurred 8 days after completing therapy and was associated with a new infection (at a different site).

A Phase 3 cSSSI study enrolled 143 subjects prior to being discontinued due to a change in the Food and Drug Administration (FDA) Guidance for the development of antimicrobials for acute bacterial skin and skin structure infections (ABSSSI). The overall incidence of reported AEs in this study was comparable between the 2 treatment groups. The most commonly reported AEs ($\geq 10\%$ frequency in either treatment group) were nausea (26.5% omadacycline, 26.4% linezolid), headache (23.5% omadacycline, 6.9% linezolid), vomiting (8.8% omadacycline, 15.3% linezolid), diarrhea (4.4% omadacycline, 18.1% linezolid), and dizziness (10.3% omadacycline, 8.3% linezolid). Creatine phosphokinase (CK) elevation was reported in 8.8% of omadacycline-treated subjects compared to 2.8% for linezolid. AEs associated with ALT increases were reported in 4 linezolid-treated subjects (5.6%) compared to 1 omadacycline subject (1.5%). Six linezolid subjects (8.3%) reported rash compared to 1 subject (1.5%) on omadacycline. Four subjects experienced serious adverse events (SAEs) (3 omadacycline and 1 linezolid). The 3 omadacycline SAEs consisted of small bowel obstruction, large left pleural effusion, and worsening depression. The 1 linezolid SAE consisted of worsening right hand cellulitis.

For full details of safety findings in nonclinical and clinical studies, see the IB ([Paratek, 2014](#)).

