16.1.3.2 Clinical Chemistry

The analytes indicated in the table below (Table 6) below will be measured at the Central Laboratory.

Table 6 Clinical Chemistry Panel

Blood glucose	ALT	LDH
Urea	AST	CK
Creatinine	AP	(CK isoenzyme testing as required)
Sodium	Total bilirubin	Calcium
Potassium	Total protein	Phosphate
Chloride	Magnesium	Cholesterol
Bicarbonate	Albumin	Uric Acid
		GGT
		Amylase
		Lipase

ALT = alanine aminotransferase; AST = aspartate aminotransferase; AP = alkaline phosphatase; LDH = lactate dehydrogenase; CK = creatine phosphokinase; GGT = gamma-glutamyl transpeptidase.

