22.7.4 Laboratory Tests

The following variables will be analyzed descriptively:

- Laboratory variables by visit
- Change from Screening of laboratory variable by visit
- Clinically notable laboratory values (meeting predefined criteria specified in the SAP) by visit

Listings of individual subject laboratory data will be generated. Values meeting predefined criteria for being clinically notable will be flagged within the listings.

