Appendix 4 Directionality of Worst Laboratory Parameters

Laboratory Test	Parameter	Worst Value
Hematology	Hematocrit	Lowest value
	Red blood cell count	Lowest value
	Mean cell hemoglobin	Lowest value
	Mean cell hemoglobin concentration	Lowest value
	Hemoglobin	Lowest value
	Mean cell volume	Lowest value
	White blood cell count	Lowest value
	Platelets	Lowest value
	Neutrophils	Lowest value
	Lymphocytes	Lowest value
	Monocytes	Lowest value
	Eosinophils	Highest value
Chemistry	Basophils	Lowest value
	Albumin	Lowest value
	Alkaline phosphatase	Highest value
	Alanine aminotransferase (ALT/SGPT)	Highest value
	Amylase	Highest value
	Aspartate aminotransferase (AST/SGOT)	Highest value
	Urea	Highest value
	Bicarbonate	Lowest value
	Calcium	Both highest value and lowest value
	Cholesterol	Highest value
	Chloride	Both highest value and lowest value
	Creatinine	Highest value
	Creatine kinase (CK)	Highest value
	Gamma-glutamyl transpeptidase (GGT)	Highest value
	Blood glucose	Both highest value and lowest value
	Lactate dehydrogenase (LDH)	Highest value
	Lipase	Highest value
	Magnesium	Both highest value and lowest value
	Phosphate	Both highest value and lowest value
	Potassium	Both highest value and lowest value
	Sodium	Both highest value and lowest value
Coagulation	Total bilirubin	Highest value
	Total protein	Lowest value
	Uric acid	Highest value
	International normalized ratio (INR)	Highest value

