Appendix 5 Modified Division of Microbiology and Infectious Diseases Adult Toxicity Table

The DMID Adult Toxicity Table (21-NOV-2007) was modified to exclude the clinical component of the toxicity grading because clinical signs and symptoms related to abnormal laboratory values are not collected in this study. In addition, Grade 0 was added to the table so that shifts from normal could be analyzed. Grades for enzymes were modified as indicated in the table below.

For toxicity grades based on a multiple of the ULN, the normal range from the central laboratory will be applied.

For toxicity grades based on fixed values, the grades will be assigned regardless of the normal actual range values from the central laboratory. For example, a hemoglobin value of 10.0 gm/dL will be assigned a grade of 1 toxicity, even if the lower limit of normal from the laboratory was 9.8 gm/dL.

HEMATOLOGY					
	Grade 0	Grade 1	Grade 2	Grade 3	Grade 4
Hemoglobin (gm/dL)	> 10.5	9.5-10.5	8.0-9.4	6.5-7.9	< 6.5
Absolute Neutrophil Count (count/mm ³)	> 1500	1000-1500	750-999	500-749	< 500
Platelets (count/mm ³)	≥ 100,000	75,000-99,999	50,000-74,999	20,000-49,999	< 20,000
WBCs (count/mm ³)	1000-10,999	11,000-12,999	13,000-14,999	15,000-30,000	> 30,000 or < 1,000

CHEMISTRY

	Grade 0	Grade 1	Grade 2	Grade 3	Grade 4
Hyponatremia (mEq/L)	> 135	130-135	123-129	116-122	< 116
Hypernatremia (mEq/L)	< 146	146-150	151-157	158-165	> 165
Hypokalemia (mEq/L)	> 3.4	3.0-3.4	2.5-2.9	2.0-2.4	< 2.0
Hyperkalemia (mEq/L)	< 5.6	5.6-6.0	6.1-6.5	6.6-7.0	> 7.0
Hypoglycemia (mg/dL)	≥ 65	55-64	40-54	30-39	< 30
Hyperglycemia (mg/dL) (nonfasting and regardless of prior history of diabetes)*	< 116	116-160	161-250	251-500	> 500
Hypocalcemia (mg/dL) (corrected for albumin)	> 8.4	8.4-7.8	7.7-7.0	6.9-6.1	< 6.1
Hypercalcemia (mg/dL) (correct for albumin)	≤ 10.5	10.6-11.5	11.6-12.5	12.6-13.5	> 13.5
Hypomagnesemia (mEq/L)	> 1.4	1.4-1.2	1.1-0.9	0.8-0.6	< 0.6
Hypophosphatemia (mg/dL)	≥ 2.5	2.0-2.4	1.5-1.9	1.0-1.4	< 1.0
Hyperbilirubinemia (total bilirubin)	< 1.1×ULN	1.1-1.5×ULN	> 1.5- 2.5×ULN	> 2.5-5×ULN	> 5×ULN
Urea	< 1.25×ULN	1.25-2.5×ULN	> 2.5-5×ULN	> 5-10×ULN	> 10×ULN
Hyperuricemia (uric acid) (mg/dL)	< 7.5	7.5-10.0	10.1-12.0	12.1-15.0	> 15.0
Creatinine	< 1.1×ULN	1.1-1.5×ULN	> 1.5- 3.0×ULN	> 3.0-6×ULN	> 6×ULN

*The DMID toxicity table reports hyperglycemia detected in nonfasting specimens obtained from subjects with no prior diabetes.

ENZYMES

	Grade 0	Grade 1	Grade 2	Grade 3	Grade 4

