AST (SGOT)	< 1.25×ULN	1.25-2.5×ULN	> 2.5-5×ULN	> 5-10×ULN	> 10×ULN
ALT (SGPT)	< 1.25×ULN	1.25-2.5×ULN	> 2.5-5×ULN	> 5-10×ULN	> 10×ULN
GGT	< 1.25×ULN	1.25-2.5×ULN	> 2.5-5×ULN	> 5-10×ULN	> 10×ULN
Alkaline Phosphatase	< 1.25×ULN	1.25-2.5×ULN	> 2.5-5×ULN	> 5-10×ULN	> 10×ULN
Amylase	< 1.1×ULN	1.1-1.5×ULN	> 1.5-2.0×ULN	> 2.0-5.0×ULN	> 5.0×ULN
Lipase	< 1.1×ULN	1.1-1.5×ULN	> 1.5-2.0×ULN	> 2.0-5.0×ULN	> 5.0×ULN

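### CK has no grade in SAP Appendix 5, so no planned output counts subjects per arm above a prespecified CK level

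*Combined protocol and SAP*

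**What the plan says.** Protocol v2.0 section 22.7.4 promises an analysis of "Clinically notable laboratory values (meeting predefined criteria specified in the SAP) by visit" and leaves the criteria to the SAP. SAP 11.4 supplies them: "Clinically notable laboratory values will be determined based on the modified Division of Microbiology and Infectious Diseases (DMID) criteria", with the grades set out in Appendix 5. The same section builds three further outputs on those grades: shift tables of grade 0 to 4 at each visit and at worst post-baseline value; a summary ("Number and percentage of subjects with at least a 2-grade increase from baseline (based on DMID criteria) will be summarized by treatment arm"); and a listing for subjects with such an increase.

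Appendix 5 is a tailored table. The SAP states that "Grades for enzymes were modified as indicated in the table below", and that a Grade 0 was added. The enzyme block covers AST, ALT, GGT, alkaline phosphatase, amylase and lipase, and its last row is "Lipase < 1.1×ULN 1.1-1.5×ULN > 1.5-2.0×ULN > 2.0-5.0×ULN > 5.0×ULN". No block contains CK.

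Elsewhere CK is treated as a routine safety analyte. Protocol Table 6 (section 16.1.3.2) includes it in the central chemistry panel, with "CK isoenzyme testing as required". Section 16.1.3 draws that panel at Screening, Days 4, 7 and 10, EOT and PTE. SAP Table 9 lists CK, and SAP Appendix 4 gives its worst direction: "Creatine kinase (CK) Highest value".

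Protocol 9.1 states that in the sponsor-terminated Phase 3 cSSSI study CK "elevation was reported in 8.8% of omadacycline-treated subjects compared to 2.8% for linezolid".

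**The concern.** The protocol asks for predefined criteria, and for CK the SAP gives none. Neither document explains the omission. SAP 11.4 has a second set of thresholds outside Appendix 5, for transaminases, bilirubin and the Hy's law criteria, but CK is not in that set either. So CK is collected at every laboratory visit and has a stated worst direction, yet no rule says how high is notable.

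At stake is a simple safety comparison: how many subjects in each arm exceeded a given multiple of ULN. A mean or median can look alike in two arms when one has more outliers, and a maximum describes a single subject. If a CK threshold is wanted after unblinding, it will be chosen with the data in view.

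**Working it through.** **Step 1. Which analytes have a grade?** SAP Table 9 lists 23 chemistry parameters. Appendix 5 grades 16 of them:

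- 10 in the chemistry block: sodium, potassium, glucose, calcium, magnesium, phosphate, total bilirubin, urea, uric acid, creatinine
- 6 in the enzyme block: AST, ALT, GGT, alkaline phosphatase, amylase, lipase

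23 − 16 = 7 have no grade: CK, LDH, bicarbonate, chloride, albumin, cholesterol and total protein. Of these seven, CK is the only one for which the protocol reports an imbalance against omadacycline.

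**Step 2. Which outputs include CK?**

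| Output (SAP section) | CK included? |
|---|---|
| Descriptive statistics by visit, change from baseline, worst post-baseline value (11.4; mean, SD, median, minimum, maximum per 8.1) | Yes |
| H flag in listings for values above normal (11.4) | Yes |
| TEAE tables by preferred term, severity and relationship (11.1) | Yes, if reported as an AE |
| Grade 0 to 4 shift tables (11.4, Appendix 5) | No |
| 2-grade-increase table and listing (11.4, Appendix 5) | No |
| Clinically notable flag (11.4, Appendix 5) | No |
| Counts above fixed ULN multiples (11.4) | No; transaminases and bilirubin only |

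The outputs that include CK are distributional summaries, individual listings, or counts of investigator-reported events. None counts subjects per arm above a stated CK level.

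**Step 3. Reproduce the protocol's figure.** Protocol 9.1 gives treated denominators of 68 (omadacycline) and 72 (linezolid). Only one integer fits each rounded percentage:

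- 6/68 = 8.82%, stated as 8.8%
- 2/72 = 2.78%, stated as 2.8%

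Fisher's exact test on 6 v 62 and 2 v 70 gives a two-sided p of 0.157.

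**Step 4. Scale, for illustration.** Assume the earlier rates carried over to 750/2 = 375 subjects per arm:

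- 375 × 6/68 = 33.1
- 375 × 2/72 = 10.4 (10.5 with the rounded 2.8%)

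That is about 33 v 10 to 11 subjects. The 375 is the planned randomised number, not the Safety population. The rates describe reported CK elevations, not crossings of a defined laboratory threshold.

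**The case against.** The best case for leaving the plan alone is that CK remains well covered. Its worst post-baseline value is summarised with median and maximum, including unscheduled visits. High values are flagged in listings. Protocol 21.1 counts laboratory observations as possible adverse events, and SAP 11.1 tabulates TEAEs by severity. The DSMC reviews laboratory data about quarterly. The earlier signal is 6 v 2 subjects, against linezolid in a different infection, and protocol 9.1 says of the Phase 2 study that laboratory changes showed no adverse pattern. Six other chemistry parameters also lack a grade, so CK was not singled out.

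All of this stands, and it rules out several stronger readings that a reader might infer:

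- That a very high CK would go unseen. A value of, say, 20 × ULN would be the maximum of the worst-value summary, or lie below a still higher one, and would be flagged H.
- That the grade tables drive decisions. Nothing in SAP 11.4 attaches a decision, hypothesis or stopping rule to a DMID grade. The synopsis describes safety assessment as summary statistics and clinical review.
- That CK elevation is an established omadacycline effect. The documents do not say so, and p = 0.16 on eight events does not show it.
- That the 33 v 10 subjects would appear nowhere. The 8.8% v 2.8% stands in the adverse-event paragraph of protocol 9.1, so the same pattern here could also show in the TEAE tables.

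The objection does not replace the missing count. AE tables depend on what investigators choose to report. An H flag does not separate a value just above normal from one many times ULN, and it appears only in listings.

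**Conclusion.** The gap is real and narrow. As written, CK has no grade, no grade shift, no 2-grade count and no clinically notable flag, so no output gives the number of subjects per arm above a prespecified CK level. CK is otherwise summarised and listed, and it is reportable as an adverse event. The primary endpoint is unaffected.

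The earlier 6/68 v 2/72 makes CK the most natural of the seven ungraded parameters to add; it supports setting a threshold in advance and no more. The 33 v 10 to 11 figure rests on those rates recurring at 375 per arm and shows scale only. The conclusion also rests on the Appendix 5 enzyme block ending at lipase, as in the published text; a CK row elsewhere in the sponsor's copy would remove the point.

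This is a cheap improvement, not a flaw that undermines the safety analysis.

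**What to change.** Before unblinding, do one of the following.

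1. Add a CK row to the enzyme block of Appendix 5 in multiples of ULN. The AST/ALT bands already there are one workable choice (< 1.25, 1.25–2.5, > 2.5–5, > 5–10, > 10 × ULN). CK then enters the shift tables, the 2-grade outputs and the clinically notable flag with no other change.
2. Or add a sentence to SAP 11.4 requiring the number and percentage of subjects per arm with post-baseline CK above fixed multiples of ULN, with the denominator stated. The model is the existing transaminase table (> 3, > 5 and > 10 × ULN, among subjects normal at baseline). This option leaves the grade-based outputs as they are.

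The cost is one table row or one sentence, and no new data. The small downside is that other bands could be argued: Appendix 5 itself uses different multiples for amylase and lipase than for AST and ALT. Fixing the bands in advance matters more than which set is chosen.

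### The worst post-baseline column of the WBC grade shift table takes the lowest count, but WBC Grades 1 to 3 exist only for high counts

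*Combined protocol and SAP*

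**What the plan says.** Section 11.4 of the SAP relies on two appendices.

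- **Direction of worst.** Appendix 4 "provides the directionality of the worst values for each laboratory parameter". Its entry for white cells is "White blood cell count Lowest value". Calcium, chloride, glucose, magnesium, phosphate, potassium and sodium are instead listed in both directions.
- **Grades.** "Clinically notable laboratory values will be determined based on the modified Division of Microbiology and Infectious Diseases (DMID) criteria" in Appendix 5. The WBC row there, in cells per mm³ from Grade 0 to Grade 4, reads "1000-10,999 11,000-12,999 13,000-14,999 15,000-30,000 > 30,000 or < 1,000".
- **Outputs.** The shift tables compare the baseline grade "versus the value at each visit and the worst post-baseline value". A separate summary counts subjects with a rise of two or more grades from baseline, but the text does not say which post-baseline value it uses.
- **Values eligible to be worst.** "All lab values (central and local) are used for determination of the overall worst post-baseline value". Section 8.6 adds that unscheduled assessments are included in the worst-overall analyses.

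**The concern.** A worst-value column should show how far each subject departed from normal. For WBC the direction in Appendix 4 runs against the grading in Appendix 5. The lowest count is chosen, and over almost the whole scale a lower count has the same grade or a milder one. A rise on treatment that later settles would leave no trace in that column.

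WBC is an infection marker, and a count above 12,000 is one of the findings that can satisfy Inclusion Criterion 5, so some subjects may well start at Grade 1 or above. At stake is whether a safety table labelled as worst post-baseline can be read as such for this test.

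**Working it through.** There is no sample size, power or alpha figure to reproduce. The check applies the Appendix 4 direction to the Appendix 5 bands.

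**Grade function g(w), Appendix 5, w in cells/mm³**

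| WBC | Grade |
|---|---|
| below 1,000 | 4 |
| 1,000 to 10,999 | 0 |
| 11,000 to 12,999 | 1 |
| 13,000 to 14,999 | 2 |
| 15,000 to 30,000 | 3 |
| above 30,000 | 4 |

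**Step 1: shape.** g was evaluated at every whole number from 1,000 to 60,000, and it never falls as w rises. So if all of a subject's post-baseline counts are at least 1,000, g(lowest count) equals the lowest grade reached.

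**Step 2: when a high-side grade can appear.** The lowest count has Grade 1, 2 or 3 only if every post-baseline count is at least 11,000. It has high-side Grade 4 only if every count exceeds 30,000.

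**Step 3: illustrative post-baseline series.**

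| Counts | SAP rule: g(lowest) | g(highest) | Highest grade reached |
|---|---|---|---|
| 9,000; 18,000; 8,000 | 0 | 3 | 3 |
| 14,000; 16,000; 32,000; 7,500 | 0 | 4 | 4 |
| 12,000; 20,000; 13,500 | 1 | 3 | 3 |
| 2,500; 1,500; 3,000 | 0 | 0 | 0 |
| 900; 5,000; 8,000 | 4 | 0 | 4 |

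The first three rows show the fault. The last row is the exception: a nadir below 1,000 is correctly shown as Grade 4, and switching simply to the highest count would lose it. The fourth row shows that the rule gains little for leucopenia. Inclusion Criterion 5 defines that as below 4,000, yet 1,000 to 3,999 is Grade 0.

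**Step 4: one subject through the tables.** Take a baseline of 12,500 (Grade 1), Day 4 at 18,000 (Grade 3) and PTE at 8,000 (Grade 0). The worst-value column shows Grade 1 to Grade 0. The Day 4 by-visit table shows Grade 1 to Grade 3, a rise of 3 − 1 = 2 grades.

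**Step 5: is WBC alone in this?** Among the analytes graded in Appendix 5:

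- Hemoglobin, neutrophils and platelets are graded low and taken at their lowest.
- Bilirubin, urea, uric acid, creatinine and the enzymes are graded high and taken at their highest.
- Sodium, potassium, glucose and calcium are graded both ways and listed both ways.
- Magnesium and phosphate are graded low and listed both ways.

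Only WBC has a direction opposed to its Grade 1 to 3 bands.

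**Step 6: which values depend on the worst-value column.** Under section 8.6, when a visit window holds several measurements, the by-visit table uses the one from the scheduled visit. Under section 11.4, a local result enters by visit only if the window has no central result. A high count from an extra or local draw can therefore be missing from the by-visit shifts. The worst-value analysis is where the SAP promises to include it, and there the lowest-value rule discards it.

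**The case against.** The best defence is that little is concealed. By-visit shift tables would show the Step 4 subject at Grade 3 on Day 4. All central and local results are listed with high, low and clinically notable flags, and WBC by visit and its change from baseline are summarised. Subjects with at least one 2-grade increase get a listing of all results for that test, and the natural reading of that sentence is any post-baseline value. All of this stands and limits the reach of the point. It does not make the worst-value column right.

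A second defence is that the SAP cites Appendix 4 straight after the descriptive statistics, and that looking for the lowest white count is a coherent search for cytopenia, in line with neutrophils, lymphocytes and platelets. That is fair for the descriptive summary. But the appendix is said to cover every parameter, the shift-table sentence uses the same term, and nothing in the SAP redefines worst as the highest grade. A programmer might choose the highest grade unprompted, but the SAP does not say so.

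A reader might go further and infer that worsening leucocytosis is hidden from the safety report, that the table would show improvement in nearly everyone, or that the 2-grade summary is also wrong. The documents do not support these. By-visit tables and listings remain. A raised WBC is only one of several alternatives in Inclusion Criterion 5, no proportion with a raised baseline count is given, and subjects starting at Grade 0 cannot improve. The SAP does not tie the 2-grade summary to the Appendix 4 worst value.

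**Conclusion.** The rule is wrong as written, within narrow limits. In the worst post-baseline column of the WBC grade shift table, every subject whose post-baseline counts are all at least 1,000 is shown at the lowest grade reached. The gap can be as large as Grade 0 shown against Grade 4 reached, as in the second series above. How many subjects would be affected cannot be estimated from the documents. It depends on how often counts rise into a graded band and also take a lower-graded value at another post-baseline time.

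This rests on reading worst in the shift-table sentence as Appendix 4 defines it, the only definition the SAP gives. The output is descriptive safety reporting; efficacy and alpha are untouched. The practical loss falls mainly on high unscheduled or local counts. The 2-grade summary shares the fault only if it is programmed from the Appendix 4 worst value. The correction should be made because the column contradicts its own label and costs almost nothing to repair.

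**What to change.** 1. In section 11.4, state that for grade shift tables the worst post-baseline value is the one with the highest toxicity grade among all central, local, scheduled and unscheduled results. This keeps a nadir below 1,000 as Grade 4 and recovers the high-side grades.
2. In Appendix 4, change the WBC entry to both highest and lowest value, as already done for sodium and potassium, so that the descriptive worst-value summary covers both directions.
3. State which post-baseline value feeds the 2-grade summary. If it is a worst value, use the definition in item 1.

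The cost is one table cell, a sentence or two of text and a small programming change. No new data are needed.
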